1.0 Specific Aims

Specific Aim 1: To test the hypothesis that GLP-1RA decreases intermuscular fat deposition in patients with stage 3-4 CKD.

Primary Outcome: We will measure intermuscular fat deposition by magnetic resonance imaging (MRI) before and after 12 weeks of dulaglutide 1.5 mg/wk. administration in patients with stage 3-4 CKD.

Specific Aim 2: To test the safety and feasibility of 12 weeks of dulaglutide 1.5 mg/wk administration as an adjunct therapy to the standard care of patients with stage 3-4 CKD.

Safety and tolerability will be evaluated throughout the study by assessment of weight change, hypoglycemic episodes, continuous glucose monitoring (only in patients with type 2 diabetes mellitus), serious adverse events (AE), treatment-emergent AE, discontinuations attributable to AE, laboratory tests, vital signs, 12-lead electrocardiograms, and allergic/hypersensitivity reactions.

2.0 Inclusion/Exclusion Criteria

We propose to study 10 patients with stage 3-4 CKD.

Inclusion criteria:

1. Patients with stage 3-4 CKD (eGFR 15-59 ml/min/1.73 m²)
2. Age \geq 18 years and \leq 75 years

Exclusion criteria:

1. Patients with type 1 diabetes mellitus
2. Patients with T2D who are on insulin therapy or who started a new antidiabetic medication within 1 month prior to study or who received incretin-based therapy within 3 months prior to study
3. BMI <25 kg/m², BMI >40 kg/m²
4. HbA1c $>8\%$ measured within 1 month prior to study, or a history of hypoglycemic episode within 1 year prior to study, or a history of diabetic ketoacidosis
5. Uncontrolled hypertension ($>200/100$ mmHg) despite optimal antihypertensive therapy
6. Arrhythmia, heart failure (NYHA class III-IV), valve disease or heart diseases other than coronary artery disease
7. History of major gastrointestinal surgery, inflammatory bowel disease, pancreatitis or cholelithiasis
8. Personal or family history of medullary thyroid cancer, or personal history of Multiple Endocrine Neoplasia (MEN)-2
9. Pregnancy, breast feeding or intention to become pregnant
10. Previous renal transplantation
11. Acute or chronic infectious diseases
12. Cancer or chemotherapy within 3 years prior to study
13. Treatment with systemic corticosteroids within 3 months prior to study
14. Known or suspected allergy to dulaglutide
15. Claustrophobia or other contraindications for MRI

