3.0 Study Enrollment and Design

The study participants will be primarily selected from Vanderbilt's outpatient clinics and the Nashville Veterans Affairs outpatient clinics. The study visits will be conducted at the Vanderbilt University Medical Center (VUMC) Department of Nephrology Outpatient Clinic and Vanderbilt University Institute of Imaging Science (VUIIS). Institutional review board approval and written informed consent will be obtained from all study subjects. Patients meeting inclusion-exclusion criteria will be identified by physician investigators and coordinators. Patients will be first approached by clinical staff. Those who express interest will be informed about the study by the study personnel. The subjects will be selected based on the above inclusion/exclusion criteria.

[figure not shown]

Figure 5.1

All participants will undergo a 4-week run-in phase followed by 12 weeks of treatment (Dulaglutide 1.5 mg/wk), followed by 4 weeks of follow up after discontinuing the study medication (Figure 5.1).

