6.0 Study Procedures

After recruitment and review of eligibility, patients who gave informed consent will undergo the following procedures:

Screening Visit: Patients will have a screening visit 4 weeks prior to the beginning of the study intervention to confirm that they meet the inclusion-exclusion criteria. Subjects will be presented detailed information regarding the study with an opportunity to discuss the study as needed for a complete consent discussion. This visit will include a medical history extracted from the patients' medical records, demographic information, a medication history, HbA1c test (for patients with T2D), 12-lead electrocardiogram, vital signs and BMI measurement, urine, or blood pregnancy test (for females of childbearing potential) and serum creatinine test to confirm eGFR. Since the presence of any metal introduces unnecessary risk for MRI, a screening X-ray exam will be performed to confirm the absence of any metal in subjects where that is a possibility.

Visit 1 (Week -4): The purpose of this visit is to determine baseline characteristics of the patients enrolled. We will review medical records, obtain dietary and physical activity recalls

and 12-lead electrocardiogram. We will measure baseline vital signs and perform anthropometric measurements and scheduled blood and urine laboratory tests. We will calculate basal HOMA-IR, QUICKI, ADIPO-IR and LAR. We will perform MRI to assess basal visceral and ectopic fat distribution characteristics and ^{31}P MRS to assess basal skeletal muscle mitochondrial function. Baseline skeletal muscle endurance will be evaluated by six-minute walk test.

Visit 2 (Week 0): Prior to the first dose of the drug, we will review medical records, measure vital signs, perform anthropometric measurements, obtain 12-lead electrocardiogram, dietary and physical activity recalls, laboratory tests in blood and urine, six-minute walk test and perform MRI and ^{31}P MRS (Table 6.1).

The first dose of the study drug Dulaglutide (Trulicity®) will be administered while the participant is at the Nephrology Outpatient Clinic. Patients will be instructed on administration and given information about the instructions for use. Participants will administer dulaglutide on a weekly basis. Safety measures and compliance will be assessed for each patient by phone calls every two weeks.

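### Exclusion 2 ties the 3-month incretin window to patients with T2D, so a patient without diabetes but with current or recent incretin exposure could enter with drug-affected pre-treatment scans

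*Protocol*

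**What the plan says.** Protocol section 2.0, Exclusion 2, is one sentence with one subject: "Patients with T2D who are on insulin therapy or who started a new antidiabetic medication within 1 month prior to study or who received". Its last clause sets the incretin window: "who received incretin-based therapy within 3 months prior to study". The three clauses are parallel and all describe the same patients, those with T2D.

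The other passages that bear on this are:

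- **Entry.** The inclusion criteria require stage 3-4 CKD and age 18 to 75. Diabetes is not required. Exclusion 3 ("BMI <25 kg/m², BMI >40 kg/m²") leaves a BMI range of 25 to 40. Section 3.0 makes the list the operative rule: "The subjects will be selected based on the above inclusion/exclusion criteria".
- **Patients without diabetes are expected.** Section 1.0 plans "continuous glucose monitoring (only in patients with type 2 diabetes mellitus"), and the screening visit in section 6.0 includes "a medication history, HbA1c test (for patients with T2D"). Both limits make sense only if some participants do not have T2D.
- **A drug window worded for everyone.** Exclusion 13 reads "Treatment with systemic corticosteroids within 3 months prior to study", with no reference to diabetes.
- **Scans.** For Visit 1 (Week -4) section 6.0 says "We will perform MRI to assess basal visceral and ectopic fat distribution characteristics". MRI is repeated at Week 0 before the first dose, at Week 12 and at Week 16.
- **Analysis.** The SAP compares values before and after dulaglutide by Wilcoxon signed-rank tests, and uses mixed models for outcomes with more than two assessments. Every participant receives dulaglutide.

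**The concern.** The protocol treats incretin use in the previous 3 months as reason enough to keep a patient with T2D out of a trial of a drug from that class. It gives no reason why such exposure would matter less for intermuscular fat, the primary outcome, in a patient without diabetes.

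If such a patient entered, the baseline would not be a drug-free one. The bias could take several forms:

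- A patient stable on an incretin drug may change little further, which pulls the estimate toward zero.
- A recent starter may still be losing fat from the earlier drug, which inflates it.
- In a patient who recently stopped, rebound could mask the effect of dulaglutide.

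With no control arm, nothing in the design separates the earlier drug's effect from that of the study drug. With at most 10 patients, one patient carries considerable weight.

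**Working it through.** **1. Scope of the clause.** Exclusions 1 and 3 to 15 were read for any other restriction on incretins, GLP-1 receptor agonists or weight-loss drugs. There is none. Exclusion 14 concerns only allergy to dulaglutide. Applied literally, the list gives:

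| Candidate | Incretin use in the previous 3 months | Result under section 2.0 |
|---|---|---|
| With T2D | Yes | Excluded (Exclusion 2) |
| Without diabetes | Yes | No criterion applies |

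**2. What the procedures add.** The screening medication history and the record reviews at Visits 1 and 2 may reveal exposure, but no criterion makes it disqualifying. The two pre-dose scans could show continuing fat loss in a recent starter. They would not reveal a blunted response in a patient stable on the drug. The SAP does not say how the Week -4 and Week 0 scans will be used together.

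**3. The SAP's own power figure.** The SAP gives no effect size or SD for intermuscular fat, so the only available arithmetic is for VAT. Inputs (SAP, Sample size): n = 10, mean change 9%, SD 9%, two-sided alpha 0.05, paired t-test. The noncentrality is √10 × 9/9 = 3.162 with 9 degrees of freedom, which gives power of 80.3%. This agrees with the SAP's statement that power is adequate, if 80% is the benchmark. The text gives no percentage, so that benchmark is an assumption.

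**4. Illustration with one exposed patient (VAT only).** Assume that one of the 10 keeps a share r of the effect and the other nine follow the SAP. The expected mean change is then mean × (9 + r)/10. At r = 0:

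- 9% × 9/10 = 8.1%
- 12.49% × 9/10 = 11.24%

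Power is for the planned test, the exact two-sided Wilcoxon signed-rank test (critical value 8 at n = 10, true size 4.88%), by simulation with 400,000 trials per cell:

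| SAP inputs (mean/SD) | No exposed patient | One exposed, r = 0 |
|---|---|---|
| 9%/9% | about 78% | about 66% |
| 12.49%/9.3% (the cited liraglutide study) | about 96% | about 87.5% |

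Other values of r at 9%/9%:

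- r = 0.75: power about 76%, mean change 9% × 9.75/10 = 8.8%.
- r = 1.5 (recent starter): power about 81%, mean change 9% × 10.5/10 = 9.5%. Here power rises because the effect is overstated.

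The count of one exposed patient and every value of r are assumptions. The documents give neither.

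**The case against.** The strongest reply is that this is hypothetical. Nothing in the documents says that CKD patients without diabetes in the recruiting clinics use incretin drugs, and a BMI range is no evidence of drug use. The list is also loosely drafted. Exclusion 4 states an HbA1c limit for everyone, although section 6.0 tests HbA1c only in patients with T2D. Whether a criterion names T2D is therefore weak evidence of intended scope, and the incretin clause may simply have been grouped with other glucose-lowering drugs. Physician investigators identify candidates, and screening takes a medication history in order to confirm eligibility, so unnoticed enrolment is unlikely. Finally, without a control arm every participant's change is already open to confounding.

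Much of this stands, and it is why the point is minor. It does not change what the rule says. An investigator who saw the exposure would still find no criterion that required exclusion.

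A reader might infer that exposed patients have been or will be enrolled, or that the primary result is biased by a known amount. The documents support neither. A reader might also carry the power figures over to the primary outcome. They concern VAT, and the loss depends on the inputs: about 12 points at 9%/9%, but about 8 at 12.49%/9.3%, where power stays above 80%.

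**Conclusion.** The point holds as one of wording with a possible consequence. Exclusion 2 limits the incretin window to patients with T2D, no other criterion fills the gap, and patients without diabetes are eligible. A patient without diabetes with current or recent exposure could enter, and that patient's change in intermuscular fat could be biased in either direction.

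The size is 1 of 10 (10% of the sample) for each such patient, and nil if there are none. No figure for intermuscular fat can be derived. The VAT power figures rest on assumed values for the number exposed and for the share of effect kept, and show only that a single patient can matter at this sample size. It would go too far to say that the before-after comparison is confounded by this clause. Exposure that ended well before Week -4 may have little effect, and the sponsor may have meant the window for everyone. The improvement is optional and cheap.

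**What to change.** Reconcile the scope of the clause. Move the existing incretin exclusion, with its existing window, out of Exclusion 2 and state it as a separate criterion for all participants, in the form that Exclusion 13 uses for corticosteroids. Leave the insulin and new-antidiabetic clauses with T2D. Check the criterion against the screening medication history.

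The cost is a one-line eligibility amendment with no new procedure. The downside is that an otherwise eligible candidate may be lost.

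The documents do not say whether enrolment is complete. If it is, report any incretin exposure before the Week -4 and Week 0 scans in the baseline table, and give the primary result with and without such patients. That costs one table line and, if there are any such patients, one repeat of the primary analysis.

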3.0 Study Enrollment and Design

The study participants will be primarily selected from Vanderbilt's outpatient clinics and the Nashville Veterans Affairs outpatient clinics. The study visits will be conducted at the Vanderbilt University Medical Center (VUMC) Department of Nephrology Outpatient Clinic and Vanderbilt University Institute of Imaging Science (VUIIS). Institutional review board approval and written informed consent will be obtained from all study subjects. Patients meeting inclusion-exclusion criteria will be identified by physician investigators and coordinators. Patients will be first approached by clinical staff. Those who express interest will be informed about the study by the study personnel. The subjects will be selected based on the above inclusion/exclusion criteria.

[figure not shown]

Figure 5.1

All participants will undergo a 4-week run-in phase followed by 12 weeks of treatment (Dulaglutide 1.5 mg/wk), followed by 4 weeks of follow up after discontinuing the study medication (Figure 5.1).

6.0 Study Procedures

After recruitment and review of eligibility, patients who gave informed consent will undergo the following procedures:

Screening Visit: Patients will have a screening visit 4 weeks prior to the beginning of the study intervention to confirm that they meet the inclusion-exclusion criteria. Subjects will be presented detailed information regarding the study with an opportunity to discuss the study as needed for a complete consent discussion. This visit will include a medical history extracted from the patients' medical records, demographic information, a medication history, HbA1c test (for patients with T2D), 12-lead electrocardiogram, vital signs and BMI measurement, urine, or blood pregnancy test (for females of childbearing potential) and serum creatinine test to confirm eGFR. Since the presence of any metal introduces unnecessary risk for MRI, a screening X-ray exam will be performed to confirm the absence of any metal in subjects where that is a possibility.

Visit 1 (Week -4): The purpose of this visit is to determine baseline characteristics of the patients enrolled. We will review medical records, obtain dietary and physical activity recalls

and 12-lead electrocardiogram. We will measure baseline vital signs and perform anthropometric measurements and scheduled blood and urine laboratory tests. We will calculate basal HOMA-IR, QUICKI, ADIPO-IR and LAR. We will perform MRI to assess basal visceral and ectopic fat distribution characteristics and ^{31}P MRS to assess basal skeletal muscle mitochondrial function. Baseline skeletal muscle endurance will be evaluated by six-minute walk test.

Visit 2 (Week 0): Prior to the first dose of the drug, we will review medical records, measure vital signs, perform anthropometric measurements, obtain 12-lead electrocardiogram, dietary and physical activity recalls, laboratory tests in blood and urine, six-minute walk test and perform MRI and ^{31}P MRS (Table 6.1).

The first dose of the study drug Dulaglutide (Trulicity®) will be administered while the participant is at the Nephrology Outpatient Clinic. Patients will be instructed on administration and given information about the instructions for use. Participants will administer dulaglutide on a weekly basis. Safety measures and compliance will be assessed for each patient by phone calls every two weeks.

Visit 3 (Week 12): We will perform the same procedures as week 0 at week 12 (Table 6.1). Study drug administration will be terminated with the last dose given within 7 days before Visit 3.

Visit 4 (Week 16): We will perform the same procedures as week 0 at week 16 (Table 6.1).

METHODS

Anthropometric Measurements:

1. Weight
2. Height
3. Waist circumference (measured at the midpoint between the top of the iliac crest and the lower margin of the last palpable rib in the mid axillary line (inch))
4. Hip circumference (measured at the largest circumference of the buttocks (inch))
5. Waist-to-hip ratio (waist circumference (inches)/hip circumference (inches))
6. Body mass index will be calculated by the following formula:
$$\text{BMI} = \text{weight (kg)}/\text{height}^2 (\text{m}^2)$$

Research Laboratory Measurements:

Subjects will be asked to come to the VUMC Department of Nephrology Outpatient Clinic in the morning under fasting conditions for blood and urine sampling. All blood and urine sampling will be performed at the VUMC Nephrology Outpatient Clinic. After blood sampling, samples for serum creatinine and hemoglobin will be transported at room temperature and all other samples will be transported on ice and centrifuged at 3,000 revolutions/min for 15 min before being kept frozen at -80°C . The following parameters will be assessed in blood.

1. Fasting plasma glucose (by glucose oxidase method (Glucose analyzer 2; Beckman Coulter, Brea, CA))
2. Fasting insulin (by double-antibody radioimmunoassay (MilliporeSigma))
3. Fasting free fatty acids (by Methanolic HCl from Supelco (Cat. 3-3051); Measured by GC-FID from Agilent)

4. Leptin (by MILLIPEXMAP Human Serum Adiponectin Panel A kit (MilliporeSigma))
5. Adiponectin (by MILLIPEXMAP Human Serum Adiponectin Panel A kit (MilliporeSigma))
6. Creatinine (will be studied in The Vanderbilt Clinic (TVC) Patient Lab)
7. Hemoglobin (will be studied in TVC Patient Lab)
8. Albumin (by bromcresol green technique)
9. High-sensitivity C-reactive protein (by high-sensitivity particle enhanced turbidometric Unicel Dxl Immunoassay system (Beckman Coulter))
10. Total cholesterol (enzymatically (Cliniqa, San Marcos, CA))
11. Triglycerides (enzymatically (Cliniqa, San Marcos, CA))
12. HDL-C (enzymatically (Cliniqa, San Marcos, CA))

We will assess the following parameters in spot urine samples.

1. Protein (will be studied in TVC Patient Lab)
2. Albumin (Albuwell Hu ELISA kit from Exocell)
3. Creatinine (Creatinine Companion kit from Ethos Biosciences)
4. Sodium (IL 943 flame photometer, Instrumentation Laboratory, [name])

Albumin/creatinine ratio (mg/g) and protein/creatinine ratio (mg/g) will be calculated in spot urine samples.

eGFR will be calculated by the following formula:

CKD-EPI creatinine equation: eGFR: $141 \times \min(SCr/\kappa, 1)^\alpha \times \max(SCr/\kappa, 1)^{-1.209} \times 0.993^{\text{Age}} [\times 1.018 \text{ if female}] [\times 1.159 \text{ if black}]$, where SCr is serum creatinine (in mg/dL), κ is 0.7 for females and 0.9 for males, α is -0.329 for females and -0.411 for males, min is the minimum of SCr/ κ or 1, and max is the maximum of SCr/ κ or 1¹.

Systemic and peripheral IR will be calculated by the following formulas:

HOMA-IR= Fasting plasma glucose (mmol/L) \times Fasting insulin (μ U/L)/22.5

QUICKI= $1/[\log (\text{Insulin } \mu\text{U/mL}) + \log (\text{Glucose mg/dL})^2]$.

Adipose tissue IR will be calculated by the following formula:

ADIPO-IR= Fasting FFA concentration (mmol/L) \times fasting insulin concentration (pmol/L)³.

Individual FFA concentrations of palmitic, oleic, linoleic, linolenic, eicosapentaenoic, docosahexaenoic, palmitoleic, palmiteladic, arachidonic, myristic, elaidic and stearic acid will be added to calculate total FFA³.

Adipose tissue dysfunction will be calculated by the following formula:

LAR: Leptin (ng/ml)/adiponectin (mg/ml)⁴.

Magnetic Resonance Imaging and Intermuscular Fat (IMAT) Measurements

On the same day as the VUMC Nephrology Outpatient Clinic Visits, patients will undergo MRI to measure VAT and IMAT. Intermuscular fat will be calculated using consecutive cross-sectional images of the mid-thigh region between the patella and ischial spine. The analysis will be performed in all the quadriceps muscle heads using a custom-written Matlab (Mathworks, Natick, MA) program, as previously described^{5,6}. IMAT will be defined as the fat beneath the deep fascia of the muscle. IMAT infiltration will be quantified as the ratio between IMAT and muscle volumes⁶.

³¹P Magnetic Resonance Spectroscopy

We will measure *in vivo* knee extensor's mitochondrial function using ³¹P-MRS to obtain the phosphocreatine recovery time constant, a measure of mitochondrial function, as we described previously⁶. During the 2 days prior to testing, we will ask that subjects 1) to perform no moderate or heavy intensity exercise within 1 day of testing; 2) not to consume alcohol within the 1 day prior to testing; 3) not to consume caffeine or use tobacco within 6 hours prior to testing; and 4) not to eat a meal 3-6 hours before testing. Mitochondrial function will be evaluated using the non-invasive technique ³¹P-MRS, which provides the quantification and kinetics of phosphocreatine (PCr), other phosphate-energy carrier molecules, and inorganic phosphate in limb muscles. Each subject will lie prone for approximately 30 minutes with a coil positioned over the belly of the vastus lateralis muscle. The position of the coil will be confirmed using scout localizer images and a reference positioned within the center of the coil (Figure 6.1.A).

[figure not shown]

Figure 6.1

After basal measurements, subjects will be asked to perform cycles of knee extension and rest using a research exercise device. Measurements will be recorded during the exercise protocol (approximately 90 seconds) and for additional 5 minutes (recovery period). We will repeat the exercise and recovery cycle at least two times. Spectra will be used to evaluate the kinetics of PCr. The primary endpoint will be the half-time of PCr recovery (time to achieve half of basal concentration during the recovery period). A spectra obtained by the investigators is shown in Figure 6.1.B. This method is reliable and reproducible and has been considered the “gold standard” to measure mitochondrial function^{7,8}.

Six-Minute Walk Test

On the same day of VUMC Nephrology Outpatient Clinic Visits, we will measure physical performance by the six-minute walk test. This test will be performed as previously

described ^{9, 10}. Briefly, patients will be instructed to walk a 30-meter corridor at a self-determined pace for a total of 6 minutes. Patients will be allowed to rest briefly by leaning against the wall or sitting during the test, or to stop prematurely if they are unable to complete the test. There will be no practice test, warm up period, or incentive provided for performance. The distance in meters will be recorded. Patients will not be encouraged to perform the test, but they will be informed about the time remaining. The detailed time schedule of the study procedures is shown in Table 6.1.

Study Drug Administration

Dulaglutide (Trulicity®) will be supplied as a 1.5 mg/0.5 mL single dose pen-injector for subcutaneous administration. Drug will be dispensed by the study personnel. Drug will be provided to the participant as labelled by the participant's name at one dispence/monthly. A sharps container and injection cleaning supplies will be provided to the participant. Each participant will be instructed how to self-administer the study drug. Patients will be asked to administer dulaglutide subcutaneously once weekly, on the same day of the week, independent of meals, at any time of the day (but always at the same time of the day in subsequent administrations) in abdomen, thigh or upper arm and will be advised to rotate the injection site. In T2D patients who are using concomitant insulin secretagogues (i.e., sulfonylurea), the dose of the insulin secretagogues will be reduced (i.e., by one-half) to reduce the risk of hypoglycemia.

Dietary recall

The participants will be asked to list the food and beverages you consume for 2 days (one weekday and one weekend day) and bring it back at your next visit (dietary recall). We will ask the patient to complete a diet recall form. The form is to ease patients to remember their diet and to increase the accuracy of diet recalls. Patients will be given the forms prior to their study visits. They will document everything they eat and drink on a weekday and on a weekend day.

Activity Monitor (Physical Activity Recall)

The physical activity monitor is about the size of a watch. It is worn on your non-dominant wrist (for example your left wrist if you are right-handed). Participants will wear this monitor for 7 days. They will wear it 24 hours per day, including when they sleep, shower, or do any other activities. We will also provide a physical activity log to document physical activity during the day.

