Title of the study: Effects of Glucagon-Like Peptide-1 Agonists on Metabolism and Ectopic Fat Deposition in Chronic Kidney Disease: A Pilot and Feasibility Study

NCT number: NCT05254418

Date: 12/02/2024

Statistical Considerations

Sample size

Up to ten subjects will be enrolled to participate in the study. This study design will provide preliminary data on the effects of GLP-1RA on ectopic fat deposition, mitochondrial function, and physical performance in patients with CKD. We performed a power analysis based on the study by Neeland et al, investigating the effects of liraglutide on VAT in overweight and obese patients. According to their results, liraglutide treatment for a median of 36 weeks results in a mean change in VAT of 12.49%, with a standard deviation of 9.3%. Using their findings, we estimated the power for detecting changes in VAT based on a sample size of 10 using paired-t test (Figure 10.1). For a sample size of 10, there is adequate power to detect a mean change of 9% or more in VAT with a standard deviation of 9% and alpha value of 0.05.

Figure shows how the power would change if the sample size were to be extended to 20 following the pilot study.

[figure not shown]

Figure 10.1

[figure not shown]

Figure 10.2

Data Analysis

The comparison of primary and secondary outcomes, specifically the differences in (a) intermuscular fat deposition, (b) adipose tissue insulin resistance, (c) peripheral insulin resistance, (d) visceral tissue fat deposition, (e) phosphocreatine recovery time constant, (f) physical performance score, before and after dulaglutide administration will be assessed using Wilcoxon signed-rank tests.

Generalized linear mixed effects models will be used to examine associations of GLP-1RA with changes in outcomes with more than 2 repeated assessments. All p-values will be two-tailed ($\alpha=0.05$) and analyses will be completed using Stata 16.

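### The HOMA-IR formula gives insulin in μU/L, a factor of 1000 away from the μU/mL used in QUICKI and from the scale its 22.5 divisor implies; probably a prefix slip, and minor

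*Protocol*

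**What the plan says.** Protocol section 6.0, under the research laboratory measurements, introduces the two indices with "Systemic and peripheral IR will be calculated by the following formulas". The first begins "HOMA-IR= Fasting plasma glucose (mmol/L", which is multiplied by "Fasting insulin (μ U/L)/22.5". QUICKI, on the next line, takes insulin in μU/mL and glucose in mg/dL. ADIPO-IR, a little further down, uses "fasting insulin concentration (pmol/L", that is, pmol/L.

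One insulin assay is listed: "Fasting insulin (by double-antibody radioimmunoassay (MilliporeSigma". No reporting unit is given for it.

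These are working rules. For Visit 1 the protocol says "We will calculate basal HOMA-IR, QUICKI, ADIPO-IR and LAR", and Table 6.1 schedules HOMA-IR at Visits 1 to 4. The SAP's Data Analysis section lists "c) peripheral insulin resistance" among the outcomes to be compared before and after dulaglutide by the Wilcoxon signed-rank test. It names no index for that outcome.

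**The concern.** Two adjacent formulas draw on one insulin measurement, and their insulin units differ by a factor of 1000. The constant 22.5 has meaning only for one choice of unit, so the unit is part of the definition of HOMA-IR.

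The stake is descriptive. The SAP presents the study as a source of preliminary data, and such data are used through their levels, changes and standard deviations. If the formula were applied as printed, these would be on a scale that no reader could set beside other HOMA-IR values.

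**Working it through.** **Inputs from the protocol (section 6.0).** HOMA-IR: glucose in mmol/L, insulin in μU/L, divisor 22.5. QUICKI: insulin in μU/mL, glucose in mg/dL. The documents state no HOMA-IR value, range or cut-off, so there is no figure of the plan's own to reproduce.

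**Assumed inputs.** The glucose and insulin pairs below are illustrative and do not come from the documents.

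**Unit conversion.** 1 μU/mL = 1000 μU/L = 1 mU/L.

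**Step 1: size of the discrepancy.** HOMA-IR = glucose × insulin / 22.5.

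| Glucose (mmol/L) | Insulin (μU/mL) | As written, insulin in μU/L | Insulin in μU/mL |
|---|---|---|---|
| 4.5 | 5 | 4.5 × 5,000 / 22.5 = 1000 | 1.00 |
| 5.0 | 10 | 5.0 × 10,000 / 22.5 = 2222 | 2.22 |
| 5.5 | 10 | 5.5 × 10,000 / 22.5 = 2444 | 2.44 |
| 5.5 | 15 | 5.5 × 15,000 / 22.5 = 3667 | 3.67 |
| 7.0 | 25 | 7.0 × 25,000 / 22.5 = 7778 | 7.78 |

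The ratio is 1000 in every row, because it comes only from the unit.

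**Step 2: which line is out of scale.** The index equals 1 when glucose × insulin = 22.5. Take that point as a reference and assume glucose of 5 mmol/L (about 90 mg/dL); insulin is then 22.5 / 5 = 4.5 in the formula's unit. I read the 2 that ends the QUICKI formula as a citation mark, like the 3 and 4 that end ADIPO-IR and LAR, and use base-10 logs.

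- As written, 4.5 μU/L = 0.0045 μU/mL. QUICKI = 1 / (log 0.0045 + log 90) = 1 / (−2.35 + 1.95), about −2.5. A negative value is meaningless for this index.
- With μU/mL, insulin is 4.5 μU/mL. QUICKI = 1 / (0.65 + 1.95) = 0.38.

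The divisor therefore fits the unit printed for QUICKI and does not fit the one printed for HOMA-IR.

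**Step 3: what a constant factor changes.** Suppose glucose stays at 5.5 mmol/L and insulin falls from 15 to 10 μU/mL.

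- Absolute change: 2.44 − 3.67 = −1.22 with μU/mL; 2444 − 3667 = −1222 as written (from unrounded values).
- Percent change: −1.22 / 3.67 = −33% in both cases.
- Signed-rank test: multiplying every difference by 1000 leaves signs and ranks as they were. A simulated sample of 10 pairs gave p = 0.00195 on both scales.
- Raw-scale mixed model: coefficient and standard error are both multiplied by 1000, so their ratio is unchanged. On the log scale only the intercept moves.

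**The case against.** The strongest reply has five parts.

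1. **Different indices may use different units.** This is right. The same two lines take glucose in mmol/L and in mg/dL, and ADIPO-IR takes insulin in pmol/L; none of that is an error. The mismatch with QUICKI only draws attention to the line. The point rests on the divisor as well, as in Step 2, and that step uses an assumed reference value.

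2. **Per litre is not the fault.** Also right. The unit mU/L is per litre and equals μU/mL. The prefix is what does not fit.

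3. **The unit might have been damaged when the text was read from PDF.** This cannot be excluded for a single Greek prefix, but it is speculative: the unit is legible, and μU/mL is legible on the next line.

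4. **Nobody would follow it.** QUICKI needs the insulin result in μU/mL at the same visits, and a HOMA-IR in the thousands would stand out. A reader might infer that every HOMA-IR value in the trial will be reported wrongly. The documents do not support that: they give no reporting unit for the assay and do not show that staff would convert to μU/L. But the chance that an analyst would override the formula does not make it correct.

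5. **No planned inference is affected.** This stands. A reader might infer that the SAP's peripheral insulin resistance comparison is compromised. The signed-rank result does not depend on the scale, and the SAP does not say that HOMA-IR is the index for that outcome. The protocol puts HOMA-IR and QUICKI together under systemic and peripheral insulin resistance without saying which stands for which. HOMA-IR also plays no part in the primary outcome, the eligibility criteria or the power calculation.

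**Conclusion.** The formula is wrong as written, in a small way. Its insulin unit is off by exactly 1000 relative to QUICKI and to the scale that 22.5 implies. The factor of 1000 between the two lines follows from the documents alone. Placing the fault in the HOMA-IR line rests on the divisor and on the assumption that an index near 1 is a sensible reference point.

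If the formula is followed literally, HOMA-IR levels, absolute changes and raw-scale coefficients are 1000 times too large. Signed-rank p-values, percent changes, log-scale effects and model test statistics are unaffected. The likely cause is a typing slip. Minor severity.

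**What to change.** In the HOMA-IR formula in protocol section 6.0, change the insulin unit from μU/L to μU/mL, or equivalently to mU/L. Leave QUICKI and the divisor as they are. Any HOMA-IR value already calculated with insulin in μU/L can be divided by 1000; no new data are needed.

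The cost is one unit in one line. Visits, samples, assays, planned tests and sample size do not change.
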